## Design Document and Analysis Plan

Project Name: Using Letters and Emails to Increase Health Insurance Take-up in California's ACA Marketplace

Date Finalized: 6/18/2021

This document serves as a basis for distinguishing between planned (confirmatory) analysis and any unplanned (exploratory) analysis that might be conducted on project data. This is crucial to ensuring that results of statistical tests will be properly interpreted and reported. For the Analysis Plan to fulfill this purpose, it is essential that it be finalized and date-stamped before we begin looking at outcome data. Once this plan is finalized, a date is entered above, and the document is shared with the primary customer for the project.

### Project Objectives

Use direct mail and email to increase ACA marketplace take-up among low-income Californians who submitted an application, were found eligible for a \$1 per member per month (PMPM) Enhanced Silver 94 plan but had yet to enroll in a health insurance plan for the 2021 coverage year.

### Evaluation Design

#### Test Arms / Treatment Conditions:

This is a randomized design among 44,000 households who submitted a Covered California application for the 2021 coverage year and were found eligible for a \$1 PMPM Enhanced Silver 94 plan. Households were randomly assigned to one of three arms: (1) a Control group assigned to receive no letter or emails during the month of June 2021, a (2) a Generic outreach group assigned to receive a letter and email reminders about the availability of \$1 plans, or (3) a Personalized outreach group assigned to receive a letter and email reminders informing them that they are eligible for a \$1 PMPM Enhanced Silver 94 plan.

#### Total Number of Observations:

N = 44,000

. tab arm				
arm	Freq.	Percent	Cum.	
Control	11,000	25.00	25.00	
Generic	16,500	37.50	62.50	
Personalized	16,500	37.50	100.00	
Total	44,000	100.00		

#### Randomization / Assignment:

Randomization was done at the household level by Covered California staff.

#### Power:

The intervention will run for approximately four weeks in the month of June 2021. Given the short duration of the intervention, we expect the baseline health insurance take-up rate to be under 5 percent, based on prior evaluations among applicants referred by the Medicaid eligibility system. In a pairwise comparison (e.g. Control vs. Personalized treatment), we are

powered at the 80% level to detect a 0.5 percentage point difference in health insurance take-up rates.

### **Likely Effect Size:**

Based on prior letter interventions on the ACA Marketplaces, we would expect to observe an ITT effect between 0.3pp and 1.3pp.

### ***Data and Data Structure***

This section describes variables that will be analyzed, as well as changes that will be made to the raw data with respect to data structure and variables.

#### **Data:**

We will use Covered California administrative data from the 2021 coverage year, which includes consumer demographics as well as eligibility and enrollment information. To complement this core dataset, we will also use CDPS risk scores and OSHPD encounter data from 2019.

#### **Outcomes:**

This randomized evaluation has three primary outcomes: (1) an indicator for whether the household selected a Covered California plan, (2) an indicator for whether the household selected an Enhanced Silver plan and (3) an indicator for whether the household's plan selection has a \$1 PMPM net premium. We will measure outcomes at three points in time: the end of June 2021, the end of July 2021 and the end of August 2021.

Secondary outcomes will include plan effectuation, duration of coverage and estimated out-of-pocket expenses.

#### **Quality Control Checks:**

After carrying out the randomization, we checked for balance across several observable covariates, which indicated no significant differences across arms.

	Control	Generic	Personalized
Subsidy FPL %	122%	122%	121%
County-referred application	95%	95%	94%
English Language Preference	67%	67%	67%
Spanish Language Preference	28%	29%	29%
Has Email	63%	62%	62%
Head of Household Female	70%	70%	70%
Head of Household Age	42	42	42
N	11,000	16,500	16,500

#### **Anticipated Limitations:**

The main limitation with our design is that approximately 40% of households do not have an email address on file and thus cannot receive part of the treatment to which they were assigned.

## Statistical Models & Hypothesis Tests

This section describes the statistical models and hypothesis tests that will make up the analysis — including any follow-ups on effects in the main statistical model and any exploratory analyses that can be anticipated prior to analysis.

### Statistical Models:

Intent-to-treat: to estimate treatment effects, our primary analysis will be an intent-to-treat (ITT) specification, examining the effect of treatment assignment. We will estimate the effect of each treatment arm using ordinary least squares (OLS) regression. That is, we will regress the outcome of interest (e.g. take-up) for household  $i$  on the set of indicator variables for each of the treatment groups:

$$outcome_i = \alpha + \beta_1 Generic + \beta_2 Personalized_i + \varepsilon_i$$

The coefficient  $\beta_1$  will be the estimate of the causal effect of the intent to treat of the generic letter and emails. The coefficient  $\beta_2$  will be the estimate of the causal effect of the intent to treat of the personalized letter and emails. To the extent there are differences across treatment arms, we will test for equality of coefficients.

While covariates are not required to obtain unbiased estimates, they can help improve precision, so we will also estimate covariate-adjusted regressions that includes the pre-treatment covariates in the balance table above.

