### Follow-Up Analyses:

We will explore treatment heterogeneity among the following observable characteristics:

- Whether the household has an email address on file
- Age (e.g. above or below the mean)
- Language preference (e.g. English vs. non-English)
- Prior health status based on OSHPD encounter data from 2019
- Recency of application submission

For all of the heterogeneity analyses, we will interact the categories above with the treatment indicators.

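### Does the SAP need to name a standard-error estimator for its OLS models of rare 0/1 outcomes?

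*SAP*

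**What the plan says.** Under *Statistical Models* the SAP regresses each outcome on indicators for the Generic and Personalized arms: "We will estimate the effect of each treatment arm using ordinary least squares (OLS) regression". It adds "To the extent there are differences across treatment arms, we will test for equality of coefficients", and a covariate-adjusted version of the model. The primary outcomes are 0/1 variables, the first being "an indicator for whether the household selected a Covered California plan". *Inference Criteria* sets two-tailed tests at 0.05 with no multiplicity correction. No section mentions conventional, robust or any other standard errors.

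Three other statements fix the setting. *Power* says "we expect the baseline health insurance take-up rate to be under 5 percent", *Likely Effect Size* says "we would expect to observe an ITT effect between 0.3pp and 1.3pp", and *Total Number of Observations* gives arms of 11,000, 16,500 and 16,500 households.

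**The concern.** A 0/1 outcome with rate p has variance p(1−p). If the letters and emails work as the SAP expects, take-up differs between arms and so does the variance. Conventional OLS errors pool one residual variance over all three arms, so the Generic-versus-Control standard error would depend partly on how well Personalized performs. Point estimates are unaffected, but the p-values that decide significance are not.

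The direction also differs by contrast. When both treatments work, the pooled variance is too large for comparisons with the lower-rate Control arm and too small for comparing the two treated arms. An estimator left unnamed in a plan meant to be fixed before outcome data are seen also looks like a choice left open. At stake would be some power in the main ITT contrasts and a small excess of false positives in the equality test.

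**Working it through.** **Inputs.** From the SAP: n = 11,000 (C), 16,500 (G), 16,500 (P); two-sided 0.05; effects 0.3 to 1.3 pp; design difference 0.5 pp. Assumed: control rates from 1% to 5%, because the SAP gives only an upper bound.

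**The SAP's own figure.** *Power* claims 80% for 0.5 pp in a pairwise comparison. With power = Φ(0.5/SE − 1.96) and SE = √(v_C/11,000 + v_P/16,500) in pp, Control versus Personalized gives 96% at a 1% control rate (SE 0.134), 79% at 2% (0.181), 64% at 3% (0.217) and 45% at 5% (0.273). The 80% is met at about 1.9% or below. I therefore take 2% as the lead case. Whether the power statement suits a rate nearer 5% is a separate question that no choice of standard error settles.

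**Formulas.** v = p(1−p); s² = Σnv/44,000.
- Conventional SE = √[s²(1/nᵢ + 1/nⱼ)]
- Robust SE = √(vᵢ/nᵢ + vⱼ/nⱼ)
- Ratio = conventional SE / robust SE
- True size of a nominal 5% test with conventional errors = 2[1 − Φ(1.96 × ratio)]

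**Lead case, 2% / 2.5% / 2.5%.** v = 0.0196, 0.024375, 0.024375, so s² = 0.25 × 0.0196 + 0.75 × 0.024375 = 0.02318.
- Treated versus Control: conventional 0.187 pp, robust 0.181 pp, ratio 1.038. Power with conventional errors is Φ[(0.5 − 1.96 × 0.1874)/0.1805] = 76.9%, against 79.1%.
- Personalized versus Generic: conventional 0.168 pp, robust 0.172 pp, ratio 0.975, size 5.6%.

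**Other cases.**

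| C / G / P (%) | Contrast | Ratio | Conventional vs robust |
|---|---|---|---|
| all equal | any | 1.000 | size 5.0% vs 5.0% |
| 1 / 1.5 / 1.5 | treated vs C | 1.070 | power 95% vs 96% |
| | P vs G | 0.958 | size 6.0% vs 5.0% |
| 5 / 5.5 / 5.5 | treated vs C | 1.016 | power 44% vs 45% |
| | P vs G | 0.989 | size 5.3% vs 5.0% |
| 1 / 2.3 / 2.3 | treated vs C | 1.138 | power about 100% either way |
| | P vs G | 0.927 | size 6.9% vs 5.0% |
| 2 / 2 / 2.5 | G vs C | 1.045 | size 4.1% vs 5.0% |
| | P vs C | 0.997 | power 79% either way |
| 2 / 2.3 / 3.3 | G vs C | 1.104 | power 32% vs 39% |
| 1 / 1.3 / 2.3 | G vs C | 1.191 | power 49% vs 64% |

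Simulation of several of these cases (400,000 replicates each) agreed with the closed form and put the robust (HC2) size at 5.0 to 5.1%. In fitted OLS models, HC1, HC2 and HC3 agreed to about 0.00001 pp.

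**Interactions.** *Follow-Up Analyses* says "We will explore treatment heterogeneity among the following observable characteristics". With no treatment effect and subgroup shares a and b, ratio² = (a·v_a + b·v_b)/(b·v_a + a·v_b). The balance table gives 62/38 for email (*Anticipated Limitations* rounds this: "approximately 40% of households do not have an email address on file") and 67/33 for "English Language Preference" against the rest. Subgroup take-up is not given. Assuming 2% in the larger group and 3% in the smaller, size is 6.1% (email) and 6.7% (language). With the rates swapped it is 4.0% and 3.6%; with equal rates it is 5.0%.

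**The case for a change.** The best case for a change is that the plan exists to close off choices before outcomes are seen, and that one sentence would do so at no cost. The choice can also matter in a primary contrast. At an assumed 1% control rate with +0.3 pp for Generic and +1.3 pp for Personalized, the expected Generic-versus-Control z is 0.3/0.1543 = 1.94 with conventional errors and 0.3/0.1295 = 2.32 with robust ones, on either side of 1.96. At 0.5% the ratio reaches 1.33, with power 69% against 87%. Under unequal effects, then, the error need not be tiny.

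That arithmetic stands, but three things limit it. First, it needs a low control rate, sharply unequal effects and analysts who leave the errors conventional. The last is an assumption about a software default, since the SAP names no command or option. Second, the failure is conservative: it costs power for Generic and cannot produce a spurious effect against Control. Third, the anti-conservative case needs both treatments to share the same non-zero effect, in a test the SAP makes conditional on differences between the arms. The interaction figures rest on assumed subgroup rates, can go either way and concern exploratory analyses.

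**Conclusion.** The omission is real, but it is a missing detail and not an error in the plan. The SAP's text is compatible with robust standard errors, which are an ordinary choice for OLS on a 0/1 outcome, and at this sample size it makes no practical difference which standard robust version is used. Households are both randomized and analysed, so clustering raises no further issue.

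If conventional errors were used, tests against Control would be exact with no effect in either arm, and conservative or nearly exact otherwise. In the lead case the cost is about 2 points of power, 79.1 − 76.9 = 2.2. The largest cost found at a 2% control rate is about 7 points, 39 − 32, for Generic versus Control under unequal effects. The equality test would run at 5.3 to 6.0% for +0.5 pp in both arms, and up to 6.9% for +1.3 pp over a 1% control rate. No primary conclusion is shown to change.

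These sizes rest on assumed control rates of 1% to 5%. The losses would be larger below 1%, which the SAP does not exclude. The covariate-adjusted models were not calculated separately.

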### Inference Criteria, Including Any Adjustments for Multiple Comparisons:

Because we are examining a small set of outcomes, we will not perform any corrections for multiple hypothesis testing, and we will use two-tailed tests with  $p$ -values  $\leq 0.05$  to denote statistically significant effects.

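### The primary ITT regression is unadjusted and its adjusted companion omits application recency: a small, nearly free gain in precision is left unused, but nothing is in error

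*SAP*

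**What the plan says.** Under Statistical Models, the SAP calls the ITT specification its primary analysis and displays an OLS equation with an intercept and the two arm indicators. It notes that covariates are not needed for unbiasedness but may help precision, and continues: "we will also estimate covariate-adjusted regressions that includes the pre-treatment covariates in the balance table above".

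The balance table (Quality Control Checks) lists subsidy FPL %, "County-referred application", English and Spanish preference, email on file, and sex and age of the head of household. It contains neither recency nor any health measure.

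Two other places name further variables:
- Follow-Up Analyses lists "Recency of application submission" and 2019 health status among the characteristics for exploring heterogeneity.
- The Data section says "we will also use CDPS risk scores and OSHPD encounter data from 2019".

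Under Power, the trial is "powered at the 80% level to detect a 0.5 percentage point difference in health insurance take-up rates", and of the control rate the SAP says "we expect the baseline health insurance take-up rate to be under 5 percent". Likely Effect Size gives 0.3 to 1.3 percentage points (pp).

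**The concern.** The plan gives a reason to adjust and then does not apply it to the regression that decides. Every household had applied before assignment, so time since application is a baseline variable. It must be built for the subgroup analysis anyway, yet no main-effect model uses it and its balance across arms is not shown.

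Precision is not in surplus. The stated detectable difference of 0.5 pp lies inside the expected range of 0.3 to 1.3 pp, so an effect at the lower end could be missed. What is at stake is the width of the confidence intervals, and only slightly. The validity of the result is not in question.

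**Working it through.** **Inputs from the SAP.** Control 11,000 and Personalized 16,500 households, 44,000 in total (Total Number of Observations); two-sided 0.05 without multiplicity correction (Inference Criteria); 80% power for 0.5 pp (Power); baseline under 5%, with no point value (Power).

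**Assumed.** The strength of the link between recency and take-up, which the SAP does not give.

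**1. The plan's own figure.** Power = Φ[(d − 1.96·SE0)/SE1], where SE0 is the pooled and SE1 the unpooled standard error of the difference, and d = 0.5 pp.
- Baseline 1.88%: SE0 = 0.180 pp, SE1 = 0.176 pp, power 80.0%.
- Baseline 3%: power 62.5%.
- Baseline 5%: SE0 = 0.276 pp, SE1 = 0.273 pp, power 44.1%.

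The stated 80% is therefore met at a baseline of about 1.88%. No baseline is given, so the figure cannot be confirmed or refuted as such. Step 3 takes 80% as the nominal starting point.

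**2. R-squared of recency as a two-group split.** With a share f of recent applicants, take-up a (recent) and b (others), and mean m: R² = f(1−f)(a−b)²/[m(1−m)].
- Mild: f = 0.50, mean 2%, two-fold ratio (2.67% against 1.33%): 0.25 × 0.01333²/0.0196 = 0.002.
- Mild, upper end: f = 0.50, mean 5%, five-fold ratio (8.33% against 1.67%): 0.25 × 0.06667²/0.0475 = 0.023.
- Generous: f = 0.30, 6% against 1.5%, m = 2.85%: 0.21 × 0.045²/0.02769 = 0.015.
- Generous, upper end: f = 0.15, 10% against 1%, m = 2.35%: 0.1275 × 0.09²/0.02295 = 0.045.

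The assumed range is therefore 0.2% to 4.5%.

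**3. Gain from adjustment.** SE ratio = √(1−R²); power = Φ[2.80/√(1−R²) − 1.96]; equivalent extra households = 44,000 × [1/(1−R²) − 1]. This assumes that recency relates to take-up in much the same way in each arm.

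| R² | SE falls by | Nominal 80% becomes | Equivalent extra households |
|---|---|---|---|
| 0.2% | 0.1% | 80.1% | about 90 |
| 1% | 0.5% | 80.4% | about 440 |
| 2% | 1.0% | 80.8% | about 900 |
| 4.5% | 2.3% | 81.8% | about 2,070 |

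The range is for recency alone. The balance-table covariates would add to it by an amount the SAP does not allow one to estimate. Even a total R² of 10% would lift 80.0% only to 84.0%.

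**4. Chance imbalance in recency.** For a 50/50 split, one standard deviation of the difference in shares is √[0.25 × (1/11,000 + 1/16,500)] = 0.62 pp. Multiplied by the mild take-up gaps of 1.33 to 6.67 pp, it moves the estimate by about 0.008 to 0.041 pp. The unadjusted standard error already includes this variation.

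**The case against.** The strongest case against is that an unadjusted primary with a prespecified adjusted companion is standard and valid, and that the SAP describes it correctly. This stands in full. It means the point is an optional refinement, and the size of the gain agrees with that.

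Four stronger readings are tempting, and the SAP supports none of them.

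- **That the arms are visibly imbalanced, so the primary result is biased.** County referral prints as 94% in Personalized against 95% in the other two arms. Had Personalized and Control truly differed by one point, the pooled share would be 0.944 and the SE √[0.944 × 0.056 × (1/11,000 + 1/16,500)] = 0.283 pp, giving z of about 3.5. The SAP reports no significant differences, so the true gap must be smaller; the figures are printed as whole percentages. County referral and FPL are also already in the planned adjusted model. Under randomisation the unadjusted estimator is unbiased in any case.
- **That listing recency as a subgroup variable shows the plan expects it to predict take-up.** It does not. A candidate effect modifier need not be prognostic, and the SAP says only that heterogeneity will be explored.
- **That the CDPS score is a ready baseline covariate.** The Data section does not state its coverage, and the year 2019 may date only the OSHPD encounter data.
- **That adjustment would repair the power statement.** Reaching 80% for 0.5 pp would need an R² of about 0.34 at a 3% baseline and 0.58 at 5%, far above anything assumed here.

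**Conclusion.** The point holds as a minor improvement. The primary regression is unadjusted, and recency, a baseline variable the plan needs anyway, is in neither main-effect model. Using it would cut standard errors by about 0.1% to 2.3% and raise a nominal 80% power by about 0.1 to 1.8 points. The figures rest on an assumed R² of 0.2% to 4.5%. The upper end needs a ten-fold take-up gap between recent and older applicants, and the mild assumptions stop at 2.3%. No test, error rate or conclusion in the plan is wrong because of this.

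**What to change.** Before outcomes are viewed, reword Statistical Models as follows:
- Name the covariate-adjusted ITT OLS regression as the primary model, with the balance-table covariates plus time since application.
- Report the unadjusted regression alongside it as a sensitivity analysis.
- Add a health covariate, such as the 2019 OSHPD measure or the CDPS score, only once it is confirmed to predate treatment, with a missing indicator where it is incomplete.

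If outcomes have already been viewed, keep the unadjusted model as primary and label the extended adjusted model as sensitivity, so that the choice of model cannot be driven by the result.

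The cost is a few sentences in the SAP. No new data collection is needed: recency must already be derived for the planned subgroup analysis.

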### Follow-Up Analyses:

We will explore treatment heterogeneity among the following observable characteristics:

- Whether the household has an email address on file
- Age (e.g. above or below the mean)
- Language preference (e.g. English vs. non-English)
- Prior health status based on OSHPD encounter data from 2019
- Recency of application submission

For all of the heterogeneity analyses, we will interact the categories above with the treatment indicators.

### Inference Criteria, Including Any Adjustments for Multiple Comparisons:

Because we are examining a small set of outcomes, we will not perform any corrections for multiple hypothesis testing, and we will use two-tailed tests with  $p$ -values  $\leq 0.05$  to denote statistically significant effects.

### Exploratory Analysis:

To the extent the treatments have an effect on primary outcomes, we will use two-stage least squares regression (2SLS) to estimate downstream effects:

- The impact of health insurance take-up on retention, for those who enrolled as a result of the intervention
- The impact of selecting an Enhanced Silver plan on out-of-pocket savings, for those who selected an Enhanced Silver plan as a result of the intervention
